10.1 Potential Risks

The potential risks and mitigations associated with the investigational devices used during this study are listed in Table 2. Risks associated with the commercially available devices used in the study are listed in the associated device labeling and are no different than a subject would experience with normal device use outside of the study.

Table 2. Risk Prevention and Mitigation

Risk with Sensors	Prevention and Mitigation

Risks with Sensors may include:
 
▪ Skin irritation or reaction to adhesives▪ Bruising▪ Discomfort▪ Redness▪ Bleeding▪ Excessive bleeding due to anticoagulants▪ Pain▪ Rash▪ Infection▪ Irritation from tapes used with glucose-sensing products▪ Raised bump▪ Appearance of a small "freckle-like" dot where needle was inserted▪ Allergic reaction▪ Syncopal episode secondary to needle insertion▪ Soreness or tenderness▪ Swelling at insertion site▪ Sensor fracture, breakage or damage▪ Minimal blood splatter associated with sensor needle removal▪ Residual redness associated with adhesive and/or tapes▪ Scarring▪ Scab▪ Blister▪ Itchiness▪ Inflammation▪ Anxiety▪ Incorrect sensor glucose reading results in incorrect diabetes management▪ Subject over-treating secondary to alarms which can result in hyperglycemia or hypoglycemia	
Prevention and mitigation include:
 
▪ Follow the provided user guides for insertions and care of sensors.▪ If a sensor site becomes infected or inflamed, the sensor will be removed and another placed in a new location▪ Base diabetes management on fingerstick readings and not on sensor glucose values.▪ Instruct to check their meter glucose if their high or low symptoms do not match their sensor alerts or sensor glucose readings in order to make diabetes treatment decisions.▪ Instruct to check their meter glucose if there are any concerns that the sensor glucose value is not accurate.▪ Instruct if there are no sensor values, no treatment decisions will be made until a BG is confirmed.

Medtronic Business Restricted

▪ Anxiety associated with insertion	
Risks with Guardian Connect Transmitter	Prevention and Mitigation

Risks with Transmitter may include:
 
▪ Skin irritation or reaction to adhesives▪ Bruising▪ Discomfort▪ Redness▪ Pain▪ Rash▪ Infection▪ Irritation from tapes used with glucose-sensing products▪ Raised bump▪ Allergic reaction▪ Soreness or tenderness▪ Residual redness associated with adhesive and/or tapes▪ Scarring▪ Scab▪ Blister▪ Itchiness▪ Inflammation	
Prevention and mitigation include:
 
▪ Follow the provided user guides▪ Train on the proper use of the transmitters.
Risks with InPen Basal Smart Cap	Prevention and Mitigation

Risks with smart cap may include:
 
▪ Hypoglycemia▪ Moderate Hyperglycemia	
Prevention and mitigation include:
 
▪ Follow the provided user guides▪ Train on the proper use of the insulin pen smart cap.
Risk with BodyGuardian MINI and Electrodes	Prevention and Mitigation

▪ Skin irritation or reaction to adhesives▪ Bruising▪ Discomfort▪ Redness▪ Pain▪ Rash▪ Raised bump▪ Allergic reaction▪ Soreness or tenderness▪ Residual redness associated with adhesive and/or tapes▪ Scab▪ Blister▪ Itchiness▪ Inflammation	
Prevention and mitigation include:
 
▪ Follow the provided user guides▪ Train on the proper use of the monitor.

10.2 Risk Minimization

Refer to "Prevention and Mitigation" column in **Table 2**.

10.3 Potential Benefits

Subjects are not expected to benefit from participation in this study; however, they may gain increased awareness of emerging technologies for diabetes management as a result of their participation.

10.4 Risk-Benefit Rationale

The data collected has the potential to facilitate the development and availability of improved Medtronic devices that may provide significant benefits to patients in the future. In light of this, we believe that the overall future potential benefits to the general population of patients with diabetes outweigh any risk to subjects who choose to participate in the investigation.

10.5 Risk Determination

In the opinion of the sponsor, this study is considered to be a non-significant risk (NSR) study. Results of an evaluation of the requirements per 21 CFR Part 812.3, led to the NSR determination as follows:

- The devices are not intended as an implant and do not present potential for serious risk to subject health, safety, or welfare.
- The devices are not to be used for supporting or sustaining human life and do not present potential for serious risk to subject health, safety, or welfare.
- The devices are not for a use of substantial importance in diagnosing, curing, mitigating or treating disease, or otherwise preventing impairment of human health and do not present potential for serious risk to subject health, safety, or welfare.
- Review of the device risk analysis did not identify potential for serious risk to subject health, safety, or welfare.

The NSR determination is also based on the commensurate safety experience of continuous glucose monitoring in commercial use. Furthermore, subjects should be instructed to make all treatment decisions based on a fingerstick glucose measurement and not on sensor glucose information provided by CGM system.

11 Adverse Events and Device Deficiencies

Throughout the course of the study, investigational centers will make all efforts to remain alert to possible reportable adverse events (AEs) or untoward findings. The study personnel will elicit reports of AEs from the subject at each visit (including phone calls) starting at the time of signing the informed

Medtronic Business Restricted

consent documenting the medical diagnosis, date of event start and end, causality (relationship to device or procedure), treatment, outcome, and description that includes the details of the event.

11.1 Definitions and Classification of Adverse Events

Medtronic uses the definitions provided in ISO 14155:2020 and 21 CFR 812 for AE definitions. Where the definition indicates “device”, it refers to any device used in the study. This might be the device under investigation, or any market released component of the system.

Severe Hypoglycemia is an event requiring assistance of another person due to altered consciousness to actively administer carbohydrate, glucagon, or other resuscitative actions^[6]. This means that the subject was impaired cognitively to the point that he/she was unable to treat himself or herself, was unable to verbalize his or her needs, and was incoherent, disoriented and/or combative.

These episodes may be associated with sufficient neuroglycopenia to induce seizure or coma. Plasma glucose measurements may not be available during such an event, but neurological recovery attributable to the restoration of plasma glucose to normal is considered sufficient evidence that the event was induced by a low plasma glucose concentration.

Diabetic Ketoacidosis/DKA diagnostic criteria: blood glucose greater than ($>$) 250 mg/dL or greater than ($>$) 13.9 mmol/L, arterial pH less than ($<$) 7.3, bicarbonate less than ($<$) 15 mEq/L, moderate ketonuria or ketonemia and requiring treatment within a health care facility^[7].

Hyperglycemic events will be recorded as DKA if the event includes the presence of all of the following:

- Arterial blood pH less than ($<$) 7.30 or serum bicarbonate less than ($<$) 15 mEq/L
- Blood glucose greater than ($>$) 250 mg/dL or greater than ($>$) 13.9 mmol/L
- Serum ketones or large/moderate urine ketones
- Symptoms such as polyuria, polydipsia, nausea, or vomiting
- Treatment provided in a health care facility

Adverse Event (AE) (ISO 14155-2020)

Any untoward medical occurrence, unintended disease or injury, or untoward clinical signs (including abnormal laboratory findings) in subjects, users or other persons, whether or not related to the investigational medical device and whether anticipated or unanticipated.

Note 1: This definition includes events related to the investigational medical device or the comparator.

Note 2: This definition includes events related to the procedures involved.

Note 3: For users or other persons, this definition is restricted to events related to the use of

Medtronic Business Restricted

investigational medical devices or comparators.

Adverse Device Effect (ADE) (ISO 14155-2020)

Adverse event related to the use of an investigational medical device.

Note 1 to entry: This definition includes adverse events resulting from insufficient or inadequate instructions for use, deployment, implantation, installation, or operation, or any malfunction of the investigational medical device.

Note 2 to entry: This definition includes any event resulting from use error or from intentional misuse of the investigational medical device.

Note 3 to entry: This includes 'comparator' if the comparator is a medical device.

Serious Adverse Event (SAE) (ISO 14155-2020)

Adverse event that led to any of the following

- a) death,
- b) serious deterioration in the health of the subject, users or other persons as defined by one or more of the following:
 - 1. a life-threatening illness or injury, or
 - 2. a permanent impairment of a body structure or a body function including chronic diseases, or
 - 3. in-patient* or prolonged hospitalization, or
 - 4. medical or surgical intervention to prevent life-threatening illness or injury or permanent impairment to a body structure or a body function
- c) fetal distress, fetal death or a congenital abnormality or birth defect including physical or mental impairment

**For the purpose of this study, Inpatient Hospitalization is defined as: admission to the hospital for a period of 24 hours or more based on urgent medical need rather than elective admission.*

Note 1 to entry: Planned hospitalization for a pre-existing condition, or a procedure required by the CIP, without a serious deterioration in health, is not considered a serious adverse event.

For the purpose of this study, the term "life-threatening" in the definition of "serious" refers to an event in which the patient was at risk of death at the time of the event; it does not refer to an event which hypothetically might have caused death if it were more severe^[8].

Serious Adverse Device Effect (SADE) (ISO 14155-2020)

Adverse device effect that has resulted in any of the consequences characteristic of a serious adverse event.

Unanticipated Adverse Device Effect (UADE) (21 CFR 812.3(s))

Any serious adverse effect on health or safety or any life-threatening problem or death caused by, or associated with, a device, if that effect, problem, or death was not previously identified in nature, severity, or degree of incidence in the investigational plan or application (including a supplementary plan or application), or any other unanticipated serious problem associated with a device that relates to the rights, safety, or welfare of subjects.

11.2 Reporting of Adverse Events

The Investigator or designee will record AEs that are device related and procedure related, SAEs, SADEs, Severe Hypoglycemia, and DKA while the subject is enrolled in the clinical study. Each AE needs to be assessed for its device or procedure relatedness. A device related AE is associated with the use of the study device (e.g. infection of sensor site or infusion set occlusion resulting in DKA). A procedure related AE is associated with testing related to the study procedures specified in the CIP.

Examples of device or procedure related AEs include:

- **Device** related (ADE): insertion site infection
- Serious adverse **device effect**: cellulitis at device insertion site requiring hospitalization
- **Procedure** related AE: bruising at fingertips from FST/ bruising at IV insertion site

Subjects participating in the study have diabetes and are expected to experience hypoglycemia and or hyperglycemia. These normal events are not expected to be reported to sponsor as this is not considered an untoward event, but rather an expected occurrence. Any glycemic excursion that meets the protocol definition of Severe Hypoglycemia or DKA is considered an untoward event and a worsening from the subject's baseline and would be reported to sponsor on an AE eCRF.

Baseline medical conditions should only be reported to sponsor on an AE eCRF if there is a worsening from the subject's baseline. For example, a subject previously diagnosed with Asthma is hospitalized for severe asthma attack would be a reportable event.

Adverse events will be documented in the subject source file and reported to sponsor on an eCRF. The investigational center is responsible for documentation of AEs including obtaining source documents related to the event, such as emergency medical technician/paramedic reports, hospital records (admission summary; lab results, test results, discharge summary) or device uploads to support the event. Source documents will be reviewed to determine if additional AEs have occurred and require reporting.

Medtronic Business Restricted

Adverse events that have not resolved at the time of the subject's discontinuation or completion of the study should have an "outcome" of Not Recovered/Not Resolved at study end in subject source and on an eCRF. The investigator should ensure that subject is aware of any follow-up or additional treatment that is required for any ongoing AE at EOS participation; however, there will be no eCRF entry for the ongoing follow-up.

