## 7.10 Safety Evaluation

### 7.10.1 Adverse Events (AE)

Descriptive summary will be used to characterize adverse events:

- Serious Adverse Events (SAE)
- Device Related AEs
- Procedure Related AEs
- Serious Adverse Device Effect (SADE)
- Unanticipated Adverse Device Effect (UADE)
- Severe hypoglycemia
- Diabetic Ketoacidosis (DKA)

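### Section 11.2 contradicts itself on whether a non-severe hypo- or hyperglycemic event caused by a study device is a reportable adverse event

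*Protocol*

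**What the plan says.** CIP section 11.2 begins with the duty to record: "The Investigator or designee will record AEs that are device related and procedure related, SAEs, SADEs, Severe Hypoglycemia, and DKA". No severity limit is attached to the device-related category. Two paragraphs later it notes that people with diabetes will have low and high glucose, and says: "These normal events are not expected to be reported to sponsor as this is not considered an untoward event, but rather an expected occurrence". The next sentence gives the exception: "Any glycemic excursion that meets the protocol definition of Severe Hypoglycemia or DKA is considered an untoward event". Such an event goes on an AE eCRF. The only glycemic example of a device-related AE in the section is "infection of sensor site or infusion set occlusion resulting in DKA".

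Table 2 (CIP 10.1) has a row for the InPen Basal smart cap, which section 6.2 classes as investigational. The row has two items: hypoglycemia, without a severity limit, and "Moderate Hyperglycemia". The list is introduced as what the risks may include. The sensor row adds wrong readings that lead to wrong diabetes management, and "Subject over-treating secondary to alarms which can result in hyperglycemia or hypoglycemia".

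CIP 13.8 and SAP 7.10.1 plan a descriptive safety summary with one item headed "Device Related AEs". No breakdown by device is stated.

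**The concern.** The non-severe glycemic harms that the risk table anticipates from the cap and the sensor are the kind of event that the second part of 11.2 tells sites not to report. Suppose a cap or app logs a basal dose wrongly, the subject acts on the record, and a non-severe low follows. One sentence of 11.2 points to an AE form and another points away from it. Up to 30 centers would each have to choose.

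At stake is what the Device Related AEs summary can mean. If most sites follow the exemption, few or no glycemic events on that line could reflect the collection rule as easily as the behaviour of the devices. This matters because the study exists to supply data for product development, and because the investigational app uses cap data and gives dose recommendations (CIP 6.2.1.2).

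**Working it through.** The plan states no AE rate or expected count, so there is no figure to reproduce. The check is a comparison of texts.

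**Step 1: the literal reading.** Section 11.1 defines an AE as an untoward medical occurrence, and an ADE as an AE related to the use of an investigational device. Section 11.2 declares ordinary hypo- and hyperglycemia not untoward. Such an event is then not an AE, so it cannot be a device-related AE. The causality assessment in 11.5, which applies to AEs, is never triggered.

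**Step 2: the other reading.** The first sentence of 11.2 has no severity floor. The notes to the ADE definition cover malfunction and use error. The exempted events are described as normal ones, which could be taken to mean background glycemia from the disease and not an excursion caused by a device. On this reading the event is recorded.

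**Step 3: apply both readings to Table 2.**

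| Device-caused event | Literal reading | Opening-sentence reading |
|---|---|---|
| Cap: hypoglycemia meeting the Severe Hypoglycemia definition | recorded | recorded |
| Cap: hypoglycemia, neither severe nor serious | not recorded | recorded |
| Cap: moderate hyperglycemia, not serious | not recorded | recorded |
| Sensor: wrong reading or over-treatment, excursion neither severe nor serious | not recorded | recorded |
| Any excursion that meets the SAE or SADE definition | recorded | recorded |

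The readings differ in the three middle rows, and those rows include both smart-cap risks in their non-severe form.

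**Step 4: look for the same information elsewhere.**

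- Sensor time below 70 and above 180 mg/dL (CIP 13.6, SAP 7.9.1) captures excursions but attributes none to a device.
- Device deficiencies (CIP 11.8, SAP 7.10.2) capture malfunctions and use errors, but the planned summary does not link them to a resulting glycemic event.
- Sites review copies of support-line calls for possible AEs (CIP 11.8). When they find a non-severe low, they are back at the contradiction in 11.2.

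**Step 5: size.** The number of lost events would need a rate of non-severe, device-caused excursions, and the documents give none. Overall exposure can only be bracketed, with years of 365.25 days:

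- 260 × 90 / 365.25 = 64 subject-years (minimum completers of 90 days).
- 500 × 100 / 365.25 = 137 subject-years (maximum enrolment, Phase 1 only).
- 500 × 280 / 365.25 = 383 subject-years (an over-estimate, since only some adults enter Phase 2).

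Exposure to the cap itself may be smaller, because section 5 allows smart pens or pens with smart caps.

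**The case against.** The strongest reply is that 11.2 need not be read as a prohibition. It exempts events it calls normal, and a low after a logging error is arguably not one. It says that excursions meeting the two definitions are reported, but not that only those are. A site could properly file a cap-caused, non-severe low under the opening sentence. This stands, and it is why the finding is a contradiction to be reconciled and not a clean exclusion.

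A reader might go further and infer three things that the documents do not support.

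- **That the cap's device-related AE count must be near zero by construction.** No cap-specific count is planned, no rate is given, and severe hypoglycemia is both within the Table 2 wording and reportable. For illustration, assume 0.01 to 0.5 Severe Hypoglycemia plus DKA events per subject-year, with 1% to 20% attributed to the cap. Expected count = subject-years × rate × share. This runs from 64 × 0.01 × 0.01 ≈ 0.01 to 383 × 0.5 × 0.2 ≈ 38. Both inputs are assumptions, and the range is too wide to support the inference.
- **That moderate hyperglycemia can never be recorded.** SAEs and SADEs are separate routes in 11.2. Hyperglycemia short of DKA that leads to an urgent inpatient stay of 24 hours or more meets the SAE definition in 11.1.
- **That a site would document nothing after a cap error.** The malfunction is a device deficiency under 11.8, applicable deficiencies reported to the support line are documented, and the glucose trace is collected. Only the link between the two is missing.

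It is also fair to say that this is a descriptive feasibility study with no hypothesis test and no planned conclusion on cap safety. That lowers the stakes. It does not remove them, because Device Related AEs is a planned safety output.

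**Conclusion.** The point holds as an internal contradiction that can undercount a planned safety summary. Under the literal reading, device-caused excursions that are neither severe nor serious are left out of Device Related AEs. These include the non-severe form of both risks listed for the smart cap, as well as glycemic harms listed for the sensor. The summary then gives no evidence on whether those risks occurred, and no other planned output fills the gap.

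The size of the undercount is unknown. It depends on how each site reads 11.2 and on an event rate that the documents do not give. The conclusion rests on two things: the AE definition in 11.1 turning on the word untoward, and the absence of any device-related exception in 11.2. Severe Hypoglycemia, DKA, SAEs, SADEs and device deficiencies are unaffected, and so is the time-in-range endpoint. The text should be corrected, but the defect does not undermine the study's main purpose.

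**What to change.** Reconcile 11.2 with its own first sentence, the ADE definition in 11.1 and Table 2.

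- **CIP 11.2:** limit the exemption to hypo- and hyperglycemia with no identified contribution from a study device. Then state that an event below the Severe Hypoglycemia and DKA definitions is recorded on an AE eCRF as device related when the site links it to a specific device deficiency, a use error, or an incorrect device, app or sensor reading.
- **Trigger:** a rating of possible should not be enough if it was given only because relatedness could not be assessed. Section 11.5 makes possible the default in that case, so a trigger on that rating alone could bring in many background excursions in continuously monitored subjects.
- **SAP 7.10.1:** show these events as a separate line under Device Related AEs, so that they are not mixed with skin and insertion-site events. Section 11.7 already sets a specific recording threshold for expected sensor-site effects, so a device-specific rule of this kind would fit the protocol's structure.

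The cost is a CIP wording change, one table line, a training note to sites and some extra AE forms. The device-related AE count will look less favourable. No visit is added, because AEs are already elicited at each visit and phone call (CIP section 11). The change concerns recording and reporting only and alters no treatment rule.

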11.3 Notification of Adverse Events

Sponsor Notification:

The investigational center staff must report all reportable AEs to Medtronic in a timely manner. All Severe Hypoglycemia, DKA, SAE, and SADEs should be reported as soon as possible (desired within 24 hours of investigator or study coordinator awareness) to Medtronic. For the previously mentioned events, the AE eCRF will be completed with all known details as soon as possible, this will serve as notification to Medtronic. If the study database cannot be accessed due to technical problems, contact the sponsor via email at [contact] and provide the known details of the event. Once the access issue has been corrected, the event should be entered onto an AE eCRF.

Source documents that support the event (e.g., clinic notes, hospital admission and discharge records, lab reports, EMT reports, ER/Urgent Care) should be provided to the sponsor via the Medtronic BOX safety folder. All source documents/medical records should be redacted of patient identifiers (full name, address, etc.) prior to providing to the sponsor. Each source page should be identified with the subject ID.

